Mild Pain or Discomfort	
Tenderness/minor ache at and/or around dressing application areaDecreased sleep or sleep qualityParesthesia (numbness, tingling, prickling, creeping sensation)
Other	
Risks to privacyLoss of data confidentiality

Potential Risks of a Blood Draw

- Discomfort
- Fainting
- Dizziness
- Bruising at the puncture site (hematoma)
- Nerve injury
- Arterial puncture or laceration

Protection Against Risks

Protected health information (PHI) of subjects in clinical investigations are kept as confidential as possible in accordance with the Health Insurance Portability and Accountability Act of 1996 (HIPAA). However, confidentiality cannot be assured. The table below lists the entities granted access to protected health information (PHI).

Entity	Reason for Access
Sponsor's Clinical Representative (Monitor)	Assess data for accuracy and completeness
Institutional Review Board (IRB)	Ensure protection of research subjects
Regulatory Authorities (e.g. Food and Drug Administration)	Audit clinical trial for Subject protection and data integrity
Investigator/Site Staff	Collection and assessment of data for accuracy and completeness

Alternatives to Participation:

Subjects are not required to participate in this research study. As an alternative to study participation, subjects will receive wound care treatment per physician discretion.

2. Trial Objectives

The primary objective of this trial is to compare the clinical outcomes between cryopreserved and lyopreserved Stravix adjunct to NPWT in the treatment of diabetes-related lower extremity complex wounds.

3. Selection and Withdrawal of Subjects

Inclusion Criteria:

- Diagnosis of a diabetes mellitus
- Men/women ≥ 21 years old
- Post-operative foot or ankle wounds sized $>4\text{cm}^2$ that have presented for <1 year
- ABI ≥ 0.5 or toe pressures >30 mmHg
- Wounds indicated for treatment with NPWT

Exclusion Criteria:

- Active Charcot arthropy
- Unable to use NPWT
- Untreated bone or soft tissue infection
- Is pregnant or plans to become pregnant
- Is nursing or actively lactating
- Developmental disability/significant psychological disorder that in the opinion of the investigator could impair the subject's ability to provide informed consent, participate in the study protocol or record study measures, including untreated schizophrenia, bipolar disorder and psychiatric hospitalization within the last 2 years.

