Randomization

Randomization will be performed using www.randomizer.org. Subjects who meet all inclusion and no exclusion criteria will be randomized in a 1:1 ratio to be treated with NPWT and either lyopreserved Stravix or cryopreserved Stravix. Study staff will use the randomization number labels contained in the envelope. The number will become the subject ID. The research staff will note treatment assignment number on the CRF. ^[17] _[SEP]

Visit Schedule

Study procedures for each phase of study are outlined below. In a later section, details on each study procedure are described, including equipment designation.

Screening

1. Explain purpose and nature of the study and obtain signature on the informed consent document.
2. Screen the subject against protocol inclusion and exclusion criteria, including all pertinent tests

(ex. ABIs), including pregnancy test

3. Complete SF-36, EuroQol 5 dimensions (EQ-5D) and PROMIS®
4. Perform neuropathy assessment
5. Randomize subject if all inclusion and exclusion criteria are met.

Baseline (-within 7 days -after screening)

1. Obtain general medical history and demographic information and social history
2. Complete a physical examination, body weight, height, BMI and vital signs, including measurement of resting heart rate, respiratory rate, and blood pressure while seated.
3. Select target study ulcer
4. Obtain complete history pertinent to DFU disease including duration of the target ulcer, previous and current treatment. Document ulcer classification.
5. Perform debridement and obtain tissue collection (up to 4 tissues and 1 bone if applicable).
6. Collect blood sample at baseline visit (approximately 10mL at each collection) for Ribonucleic Acid (RNA) gene expression.
7. Perform standardized photography and measurement of the primary study wound and, if applicable, secondary study wounds (eKare or available camera with ruler if eKare is not available) pre-debridement. Assess the post-debridement ulcer area (cm^2), perimeter (cm), and greatest depth (cm) using the inSight device (eKare, Fairfax, VA). These values are the baseline measurements for calculating wound closure rate at the two-week run-in visit.
8. Perform hyperspectral imaging of dorsal and plantar aspects of the foot.
9. Collect all relevant concomitant medication (antibiotics, antifungals and other anti-infective therapies)
10. Collect all relevant clinical lab values

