For all adverse events, the investigator must pursue and obtain information adequate both to determine the outcome of the adverse event and to assess whether it meets the criteria for classification as a serious adverse event requiring immediate notification to the Osiris Therapeutics contact. For all adverse events, sufficient information should be obtained by the investigator to determine the causality of the adverse event. The investigator is required to assess causality. For adverse events with a causal relationship to the device, follow-up by the investigator is required until the event or its sequelae resolve or stabilize at a level acceptable to the investigator, and the Osiris Therapeutics contact concurs with that assessment.

Protocol Specific AE Definition/Collection: For the purposes of this study, only AEs that are directly related to the study product, diabetes (including labs & kidney function) or wound healing (including infections related to the wound) will be collected and reported as these events may effect outcomes and analysis of data. AEs not related to the aforementioned product or diagnoses are not relevant to the subject outcomes of this research or data analysis (such as nausea, emesis, pain, constipation, diarrhea, mood disorders, respiratory diagnoses, etc). AEs that do not fall under this protocol specific definition will be assessed and treated as per standard of care. SAEs will be collected as per the usual SAE guidelines (see section on reporting SAEs). In addition, planned procedures related to the study wound for a subject during the same hospitalization (as these subjects will be recruited while in the hospital because they have an infection in their foot wound/ulcer) for incision/debridement/amputation will be considered part of their continuation of SOC and not adverse events unless a complication, new infection or new wound occurs.

Adverse Event Reporting

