For serious adverse events, the reporting period to Osiris Therapeutics or its designated representative begins from the time that the subject provides informed consent, which is obtained prior to the subject's participation in the study, i.e., prior to undergoing any study-related procedure and/or receiving investigational product, through and including 28 calendar days after the last administration of the investigational product. Any serious adverse event occurring any time after the reporting period must be promptly reported if a causal relationship to investigational product is suspected. Adverse events (serious and non-serious) should be recorded on the CRF from the time the subject has undergone one treatment through last subject visit.

Definition of an Adverse Event (AE)

An adverse event is any untoward medical occurrence in a clinical investigation subject administered a product or medical device; the event need not necessarily have a causal relationship with the treatment or usage. Examples of adverse events include but are not limited to:

- Abnormal test findings;
- Clinically significant symptoms and signs or diagnosis;
- Changes in physical examination findings;
- Hypersensitivity;
- Progression/worsening of wound.

Definition of Serious Adverse Event (SAE)

A Serious Adverse Event (SAE) is any AE that has any serious unfavorable and unintended sign, symptom, or disease temporally associated with the use of the devices, whether or not considered related, including those that:

- results in death
- is life-threatening
- requires inpatient hospitalization or causes prolongation of existing hospitalization
- results in persistent or significant disability/incapacity
- is a congenital anomaly/birth defect
- requires intervention to prevent permanent impairment or damage

Medical and scientific judgment should be exercised in determining whether an event is an important medical event. An important medical event may not be immediately life-threatening and/or result in death or hospitalization. However, the important medical event should be reported as serious, if it is determined that the event may jeopardize the subject and/or may require intervention to prevent one of the other adverse event outcomes.

Causality Assessment of Adverse Events

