The investigator's assessment of causality must be provided for all adverse events (serious and non-serious); the investigator must record the causal relationship in the CRF, as appropriate, and report such an assessment in accordance with the serious adverse reporting requirements if applicable. An investigator's causality assessment is the determination of whether there exists a reasonable possibility that the cleared medical device caused or contributed to an adverse event. If the investigator does not know whether or not medical device caused the event, then the event will be handled as "related to medical device" for reporting purposes. (see Section on Reporting Requirements). If the investigator's causality assessment is "unknown but not related to investigational product", this should be clearly documented on study records.

In addition, if the investigator determines a serious adverse event is associated with study procedures, the investigator must record this causal relationship in the source documents and CRF, as appropriate, and report such an assessment in accordance with the serious adverse event reporting requirements, if applicable.

Adverse Event Severity Assessment

The Investigator will provide an assessment of the severity of each adverse reaction by recording a

severity rating on the appropriate SAE reporting page of the subject's file. Severity, which is a description of the intensity of manifestation of the SAE, is distinct from seriousness, which implies a patient outcome or SAE-required treatment measure associated with a threat to life or functionality. Severity will be assessed according to the following scale.

If required on the adverse event case report forms, the investigator will use the adjectives MILD, MODERATE, or SEVERE to describe the maximum intensity of the adverse event. For purposes of consistency, these intensity grades are defined as follows:	
MILD	Does not interfere with subject's usual function.
MODERATE	Interferes to some extent with subject's usual function.
SEVERE	Interferes significantly with subject's usual function.

Note the distinction between the severity and the seriousness of an adverse event. A severe event is not necessarily a serious event. For example, a headache may be severe (interferes significantly with subject's usual function) but would not be classified as serious unless it met one of the criteria for serious adverse events, listed above.

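### The adverse event rules contradict one another on scope and start and, on the study-specific reading, miss non-serious harms of the research blood draws and of baseline tissue and bone sampling

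*Combined protocol and SAP*

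**What the plan says.** Four sets of statements bear on what is recorded and from when.

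- **Start.** Section 14, Adverse Event Reporting: "Adverse events (serious and non-serious) should be recorded on the CRF from the time the subject has undergone one treatment through last subject visit". The same paragraph says that the period for reporting serious events to the sponsor "begins from the time that the subject provides informed consent".
- **Scope.** Section 14, Protocol Specific AE Definition/Collection, collects and reports "only AEs that are directly related to the study product, diabetes (including labs & kidney function) or wound healing" (wound infections included). For the rest, "AEs that do not fall under this protocol specific definition will be assessed and treated as per standard of care". Serious events are exempt: "SAEs will be collected as per the usual SAE guidelines".
- **Procedures.** The Baseline list in Section 4 has "Perform debridement and obtain tissue collection (up to 4 tissues and 1 bone if applicable") at step 5, the RNA blood draw at step 6 and Stravix placement at step 11. Section 1 has a list headed "Potential Risks of a Blood Draw", which includes fainting, hematoma, nerve injury and arterial puncture. Under Causality Assessment, "if the investigator determines a serious adverse event is associated with study procedures, the investigator must record this causal relationship"; the CRF and source records are both named as the place for that entry. No matching instruction exists for non-serious events.
- **Contrary text.** The General paragraph of Section 14, Eliciting Adverse Event Information, and Non-Serious Adverse Event Reporting Requirements each speak of all adverse events. The Schedule of Events marks adverse events at BL/0.

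**The concern.** The blood draws, and the tissue and bone samples taken for laboratory analysis, serve the research: the blood goes to gene-expression work, the tissue to bacterial and molecular analyses. A trial that adds procedures should be able to report what harm they did. Here the collection categories leave study procedures out, and the recording window opens after the baseline procedures are done.

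The contradictions matter as well. One coordinator following the protocol-specific paragraph would leave a faint at a week 4 draw off the CRF. Another following the non-serious reporting paragraph would enter it. The adverse event listing would then depend partly on who filled in the form. For serious events, one paragraph sets two start times, so the sponsor's reports and the CRF may not match for the interval before treatment.

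**Working it through.** The plan states no figure on this point and no arithmetic beyond counting applies. The check sets the rules beside the order of procedures.

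**1. Scope, applied to blood draws.** Section 4 and the Schedule of Events give three scheduled research draws: baseline, week 4 and end of study (the end-of-study list makes the last depend on a wound still open and of sufficient size). There are further draws after recovery from an infection. A bruise, faint or non-serious nerve injury from venepuncture is not directly related to the product, to diabetes or to wound healing. The mention of labs under diabetes reads naturally as laboratory values, not needle injury. The paragraph also names pain among the events it regards as irrelevant. So the scope rule excludes these non-serious harms at all 3 of 3 scheduled draws and at the infection-recovery draws.

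**2. Start, applied to baseline procedures.** Taking one treatment to mean the first Stravix placement (step 11), steps 5 and 6 fall before the window. That is 1 of 3 scheduled draws and 1 of 4 scheduled tissue or bone sampling points (baseline, weeks 4 and 8, end of study, all conditional). Later procedures fall inside the window, so for them only the scope rule can exclude an event.

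The term one treatment is not defined. If the baseline debridement counted as a treatment, the sampling that follows it and the draw would fall inside the window, and this step would largely disappear. Step 1 would not change.

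**3. Which sampling harms stay collectable.** An infection or worsening of the wound that appears after placement falls in the wound-healing category and inside the window. The exemption for planned wound procedures in the same hospitalization does not extend to complications, new infections or new wounds. What is left out is a non-serious harm that arises and ends before placement, or that is unrelated to wound healing.

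**4. Serious events before treatment.** Screening may be up to 7 days before therapy starts. A serious event in that interval is reportable to the sponsor from consent, yet the CRF rule, which names serious events explicitly, has not started. The causality paragraph brings it onto the CRF only if the investigator judges it related to study procedures.

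**5. The all-events text.** The General paragraph is made subject to what follows it, and what follows includes the study-specific restriction. The eliciting and non-serious paragraphs carry no such qualifier, so they contradict the restriction outright. The BL/0 mark has no counterpart in the Baseline visit list, which contains no adverse event step. The end-of-study list provides only for following up events already reported, although that visit may include sampling and a draw.

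**The case against.** The strongest reply is that the plan already captures what matters. Serious events bypass the scope rule, are reportable from consent and have their own form, which goes to the sponsor and the IRB. A serious procedure-related event must also be noted in the source documents and CRF. Section 12 requires any adverse event to be noted in the subject's medical record, and Section 8 has monitors check source documents. Three paragraphs of Section 14 and the schedule ask for all events. Both arms follow the same sampling schedule, the safety endpoint concerns the index wound, and the protocol gives a reason for collecting selectively.

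Most of this stands, and it rules out several stronger conclusions that a reader might draw:

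- **That procedure harms in general go unrecorded.** Serious ones are captured, and so are wound complications appearing after placement.
- **That the omitted harms are hidden from the sponsor, the IRB and the final report.** Absence from the adverse event form is not absence from the medical record, to which monitors have access.
- **That multiplying samples or draws by 40 subjects sizes the problem.** That counts procedures, not harms. Bone is taken only where applicable, the schedule ties tissue to surgical debridement, end-of-study sampling is conditional, and 40 is a completion target without an enrollment cap.

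The reply does not remove the point itself. The all-events paragraphs do not override a rule written expressly for this study; at best they leave sites with two instructions. A note in the medical record is not a collected study variable.

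**Conclusion.** The point holds for non-serious events and as an internal inconsistency. On the study-specific reading, non-serious blood-draw harms are outside collection at every draw, and immediate non-serious harms of the baseline draw and baseline tissue and bone sampling precede the recording window. Separately, a serious event between consent and first treatment is reportable to the sponsor but outside the CRF window unless judged procedure-related.

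The size in events cannot be given, because the documents contain no rate for these harms. The conclusion assumes that one treatment means first Stravix placement (needed only for the start-time part) and that the study-specific paragraph governs over the general ones.

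A reader might infer that the comparison of the two Stravix arms is compromised. The documents do not support that: the sampling schedule is the same in both arms and the primary safety endpoint counts index-wound-related events. What is affected is the account of harms from the research procedures and the consistency of recording. It should be corrected, but it does not threaten the trial's main conclusions.

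**What to change.** 1. Section 14, Adverse Event Reporting: record serious and non-serious adverse events on the CRF from informed consent. This removes the dependence on an undefined term and gives both kinds of record the same start.
2. Section 14, Protocol Specific AE Definition/Collection: add events related to study procedures (blood draw, tissue and bone sampling) to the collected categories, and ask for procedure causality for non-serious events too.
3. Align the General, Eliciting and Non-Serious paragraphs with that rule, so that each states the same scope.
4. Add an adverse event step to the Baseline list, covering events since consent and the sampling itself. Widen the end-of-study step to include new events. Make the Schedule of Events agree.
5. For the arm comparison, count events from first application and list earlier ones separately. The safety endpoint in Section 6 then stays as it is.

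The cost is some wording changes and a few extra CRF entries. Changing only the start and scope sentences would not be enough, because the all-events paragraphs would still conflict with them.
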